Cases of potential drug-induced liver injury that include an elevated ALT or AST in combination with either an elevated bilirubin or clinical jaundice, as defined by Hy's law: [ALT or AST >3 x ULN + total bilirubin >2 x ULN]

- Any and any related hepatic side effects: elevations in ALT and AST >3 × ULN at the same timepoint in the study.
- Any and any related gastrointestinal (GI) disorder (MedDRA SOC: GI Disorders)
- Any and any related photosensitivity (MedDRA Preferred terms Nodular rash, Photodermatosis, Photosensitivity reaction, Pruritus, Pruritus generalized). Potential updates in those terms will be needed in case the MedDRA version changes.
- Any and any related rash (MedDRA Preferred terms Rash, Rash erythematous, Rash generalized, Rash macular, Rash maculo-papular, Rash papular, Rash pruritic, Solar dermatitis, Solar urticarial, , Sunburn, Erythema, Dry skin). Potential updates in those terms will be needed in case the MedDRA version changes.
- Angioedema (MedDRA preferred term Angioedema).
- Dizziness (MedDRA preferred term Dizziness).
- Fatigue (MedDRA preferred term Fatigue).
- Weight loss (MedDRA preferred term Weight loss).
- Increase in QT interval: In the event of a QTcF interval of >500 ms or an increase from baseline of >60 ms, a repeat ECG must be obtained within 24 hours.
- Any and any related TEAE leading to death
- Any and any related TEAE leading to treatment discontinuation

Pirfenidone — F. Hoffmann-La Roche Ltd

- Any grade 3-4 laboratory liver test results
 - o ASAT (SGOT) results
 - o ALAT (SGPT) results
 - o alkaline phosphatase results
 - o total bilirubin results

The incidence of TEAEs, related TEAEs, non-serious TEAEs, serious TEAEs, related serious TEAEs, grade 3-5 TEAEs and TEAEs leading to treatment discontinuation, dose modification or death will be summarized by treatment arm, by system organ class (SOC) and preferred term (PT) on the basis of the safety population. Frequencies and percentages of patients experiencing (at least) one event in the respective category will be presented by decreasing frequencies. If patients have more than one AE within a SOC or PT they will be counted only once for the respective SOC or PT. Additionally the total numbers of TEAEs will be provided for each SOC and overall.

Similar summary presentations will be provided for the incidence of TEAEs leading to dose reduction and drug interruption and TEAEs leading to hospitalization.

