Non serious Treatment-emergent Adverse Events with >5% frequency will be also presented by SOC and PT. In addition, Serious Treatment-emergent Adverse Events, Fatal serious TEAEs and serious TEAEs related to pirfenidone or placebo will be presented in the same table by SOC and PT.

A summary table presenting the numbers and frequency of patients with TEAEs by most extreme CTCAE Grade (Grade 1, Grade 2, Grade 3, Grade 4 and Grade 5) will be provided for each SOC and PT by treatment arm. In case the most extreme intensity is missing, it will be replaced by the initial intensity. If both most extreme and initial intensity are missing, the AE will be included in the Grade ≥3 category and a category for "missing" will be added.

Further, Kaplan-Meier curves for time to onset of first adverse event of the most relevant related TEAEs will be provided by treatment arm when the number of events are enough to do the analyses. These will include the following PTs or groups of AEs: Nausea, Diarrhoea, Weight decreased, Fatigue, Decreased appetite, and photosensitivity, or rash. In addition, the analysis will be done for the SOC GI.

All adverse event data will be listed by patient number and study day of onset including a flag variable for identifying the period of the event (double-blind treatment period or safety follow-up period). If the AE does not belong to any of the periods, the period flag will be missing.

In addition, for regulatory purpose two additional tables will be provided:

Pirfenidone — F. Hoffmann-La Roche Ltd

Frequency of adverse drug reactions occurring in patients treated with Esbriet (Pirfenidone) in clinical trials

TEAEs from day 1 of dosing until 168 days for MA39189 will be compared with the data from the phase III studies CAPACITY1 and 2 and ASCEND (restricted to first 168 days after first dose). The frequency of patients with related AEs (ADR) will be presented by System Organ Class and will be classified by their occurrences into

- Very common ((>=10% incidence rate)
- common ((>= 1% to <10% incidence rate)
- uncommon (>= 0.1% to <1% incidence rate)
- rare (>= 0.01% to <0.1% incidence rate)

Patients who withdrew from treatment during first 168 days of dosing will be censored at day of withdrawal for this analysis.

Rates of Adverse events per 100 patient years

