For safety analysis of the double-blind treatment period treatment-emergent adverse events (TEAEs) will be defined as:

 AEs that started or worsened on or after first intake of randomized treatment until last positive dose of randomized treatment + 28 days

Adverse events that are reported after informed consent but before the first intake of randomized treatment will be considered as non-treatment-emergent AEs. These might include AEs that occur during the screening period.

Post-treatment AEs are not expected to occur, but will be defined as AEs that are reported more than 28 days after the last dose of randomized treatment for patients who do not enter the 12-month safety follow-up period. Those AEs will be listed.

Pirfenidone — F. Hoffmann-La Roche Ltd

The analysis of AEs within the framework of the primary study analysis will focus on treatment-emergent AEs (TEAE).

An overview of patient safety profile will present the number and proportion of patients in each treatment arm experiencing:

- Any and any related treatment-emergent adverse events (TEAE)
- Any and any related serious treatment-emergent adverse events (serious TEAE)
- Any and any related severe treatment-emergent adverse events (TEAEs ≥ Grade 3)
- Any and any related TEAE of special interest (AESI). Adverse events of special interest for this trial include the following:

Cases of potential drug-induced liver injury that include an elevated ALT or AST in combination with either an elevated bilirubin or clinical jaundice, as defined by Hy's law: [ALT or AST >3 x ULN + total bilirubin >2 x ULN]

- Any and any related hepatic side effects: elevations in ALT and AST >3 x ULN at the same timepoint in the study.
- Any and any related gastrointestinal (GI) disorder (MedDRA SOC: GI Disorders)
- Any and any related photosensitivity (MedDRA Preferred terms Photodermatosis, Photosensitivity reaction, Pruritus, Pruritus allergic, Pruritus generalized). Potential updates in those terms will be needed in case the MedDRA version changes.
- Any and any related rash (MedDRA Preferred terms Nodular rash, Rash, Rash erythematous, Rash generalized, Rash macular, Rash maculo-papular, Rash papular, Rash pruritic, Rash follicular, Exfoliative Rash, Solar dermatitis, Solar urticarial, Sunburn, Erythema, Dry skin). Potential updates in those terms will be needed in case the MedDRA version changes.
- Angioedema (MedDRA preferred term Angioedema).
- Dizziness (MedDRA preferred term Dizziness).

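### The SAP's photosensitivity group holds nodular rash and itching terms while the sun-reaction terms sit under rash, so neither overview row measures what its label says

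*SAP*

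**What the plan says.** SAP version 3.0, section 4.6.2, lists the rows of the patient safety overview, given as numbers and proportions of patients by arm. Photosensitivity and rash are separate rows.

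- Photosensitivity: "Any and any related photosensitivity (MedDRA Preferred terms Nodular rash, Photodermatosis, Photosensitivity reaction, Pruritus, Pruritus generalized".
- Rash: several rash terms, ending with "Rash papular, Rash pruritic, Solar dermatitis, Solar urticarial, , Sunburn, Erythema, Dry skin". (I read the SAP's spelling as solar urticaria.)

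The same section plans Kaplan-Meier curves of time to first onset for selected related events: "Nausea, Diarrhoea, Weight decreased, Fatigue, Decreased appetite, and photosensitivity, or rash".

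SAP version 2.0 (October 2018), section 4.7.2, grouped the terms slightly differently:

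- Photosensitivity: "Any and any related photosensitivity (MedDRA Preferred terms Photodermatosis, Photosensitivity reaction, Pruritus, Pruritus allergic, Pruritus generalized".
- Rash: opens with "Any and any related rash (MedDRA Preferred terms Nodular rash, Rash, Rash erythematous, Rash generalized" and closes with "Exfoliative Rash, Solar dermatitis, Solar urticarial, Sunburn, Erythema, Dry skin".

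Both versions say the terms may need updating if the MedDRA version changes. Neither gives a reason for the grouping.

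The protocol handles photosensitivity and rash together in section 5.1.1.3 and Table 3, with advice to limit sun exposure. In section 5.1.1 it lists them as two separate items among the common adverse events.

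**The concern.** A patient whose only skin event is itching counts as having photosensitivity, and a patient whose only skin event is sunburn does not. Photosensitivity is part of a risk that the protocol singles out and ties to sunlight, and the overview row is where a reader will look for its rate. If the label and the content differ, both the rate in each arm and the contrast between arms describe something other than light reactions. The rash row has the mirror-image problem.

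The lists also changed between the two SAP versions. SAP version 3.0, section 4.5.8, states that the primary analysis took place in March 2019, and version 3.0 is dated July 2020. A safety grouping altered after results were available needs a recorded reason.

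**Working it through.** **Step 1: compare the lists.** The inputs are the four term lists in SAP version 2.0, section 4.7.2, and version 3.0, section 4.6.2. Terms whose placement is questionable or changed:

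| Term | Version 2.0 | Version 3.0 |
|---|---|---|
| Pruritus | photosensitivity | photosensitivity |
| Pruritus generalized | photosensitivity | photosensitivity |
| Pruritus allergic | photosensitivity | neither |
| Nodular rash | rash | photosensitivity |
| Solar dermatitis | rash | rash |
| Solar urticaria | rash | rash |
| Sunburn | rash | rash |
| Rash follicular | rash | neither |
| Exfoliative rash | rash | neither |

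Counts: version 2.0 has 5 photosensitivity and 15 rash terms, 20 in all. Version 3.0 has 5 and 12, 17 in all. One term changed group and three were dropped (20 − 3 = 17). In version 3.0, 3 of the 5 photosensitivity terms name no light reaction, and 3 of the 12 rash terms name a sun reaction.

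**Step 2: regroup.** Photosensitivity becomes Photodermatosis, Photosensitivity reaction, Solar dermatitis, Solar urticaria and Sunburn: 5 terms. The other 12 version 3.0 terms stay outside it. The combined set is the same 17 terms, so a rate pooled over it cannot change.

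**Step 3: effect on one arm's photosensitivity rate.** The SAP states no figure to reproduce. Let

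- a = patients counted only through Nodular rash, Pruritus or Pruritus generalized, with none of the five light terms;
- b = patients with a sun term but none of the five version 3.0 photosensitivity terms;
- n = 125, the planned size per arm (protocol 6.1, SAP 2.3).

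Rate as written minus rate regrouped = (a − b)/n. One patient is 1/125 = 0.8 percentage points.

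The documents give neither a nor b. Assuming a between 0 and 15 and b between 0 and 10:

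- a = 0, b = 10: (0 − 10)/125 = −8.0 points
- a = 5, b = 5: 0.0 points
- a = 10, b = 5: (10 − 5)/125 = +4.0 points
- a = 15, b = 0: (15 − 0)/125 = +12.0 points

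**Step 4: effect on the difference between arms.** The error in the risk difference is [(a − b) on pirfenidone − (a − b) on placebo]/125. Two assumed cases show that either sign is possible:

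- a equal in both arms, b = 5 on pirfenidone and 2 on placebo: −(5 − 2)/125 = −2.4 points, so the difference is understated.
- b equal in both arms, a = 10 on pirfenidone and 5 on placebo: (10 − 5)/125 = +4.0 points, so the difference is overstated.

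**The case against.** The strongest reply is that little is lost:

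- The protocol treats photosensitivity and rash as one risk in section 5.1.1.3 and Table 3, and the pooled rate is immune to moves between the groups.
- Sun reactions are not lost; they are counted in the adjacent rash row.
- SAP 4.6.2 tabulates treatment-emergent and related events by preferred term and arm, and all events are listed, so the rate of the Photosensitivity reaction term is reported unmixed.
- Photosensitivity is not among the adverse events of special interest in protocol 5.2.3, no safety testing is planned, and the regulatory frequency table is by system organ class.
- The curve wording may mean one combined curve, and the curves are drawn only if there are enough events.
- That itching is not photosensitivity is a reading of term names, since no document says so.

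Most of this stands and limits the point. It does not rescue the two separate rows, which protocol 5.1.1 also treats as separate kinds of event. Nor can a reader rebuild those rows exactly from preferred-term counts, because one patient may have several terms.

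A reader might infer that the lists were reshaped after the results were seen. The documents do not support that. The pruritus and sun-term placements date from version 2.0, before the March 2019 analysis. Only the Nodular rash move and the three drops are new, and a MedDRA update may explain the drops. The visible version 3.0 change entries (11 to 16) do not mention the lists, but the earlier part of that log is not in the text available, so it cannot be said that the change went unrecorded.

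**Conclusion.** The grouping defect is certain on the face of the lists: the separate photosensitivity and rash rows, and any separate curves, do not match their labels. The only judgement involved is reading the term names at face value.

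The consequence is not certain. A reader might infer that itching common to both arms dilutes the contrast between drug and placebo, so that the photosensitivity risk is understated. That requires equal itching in both arms and assumed rates for every term, and the documents supply neither. Size and direction are unknown. What can be said is 0.8 percentage points per misplaced patient at 125 per arm, zero net error in an arm when a = b, no change in the rate pooled over both groups from moving terms between them, and no effect on the preferred-term tables.

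This is a reporting defect worth correcting. It has no bearing on the efficacy analyses.

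**What to change.** In SAP 4.6.2:

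- Move Solar dermatitis, Solar urticaria and Sunburn to photosensitivity.
- Return Nodular rash to rash.
- Take the pruritus terms out of photosensitivity, either to their own row or to rash.
- Restore Pruritus allergic, Rash follicular and Exfoliative rash (or their current MedDRA equivalents), or state why they were dropped.
- Correct the spelling of solar urticaria and the empty entry in the rash list.
- State whether the photosensitivity and rash curve is one curve or two.

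With pruritus in its own row and the three terms restored, the groups hold 5 photosensitivity, 12 rash and 3 pruritus terms: 20 in all, as in version 2.0.

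Re-run the overview rows, including the overview by MMF subgroup (SAP 4.5.4) and the safety follow-up overview (SAP 4.7), and any separate Kaplan-Meier curves. Because this regrouping is itself post hoc and matches neither SAP version, footnote the results under the version 2.0 grouping.

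The cost is editing two term lists and repeating these outputs. The downside is that the figures will differ from tables already produced.

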4.6.2 Trial Treatment Discontinuation

Patients must discontinue trial treatment if they experience any of the following:

- Pregnancy
- Hepatic or renal impairment
- LFT elevations that require discontinuation
- Angioedema

The primary reason for early trial treatment discontinuation should be documented on the appropriate eCRF. Patients who discontinue trial treatment prematurely will not be replaced.

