5.1.1.4 Angioedema

Reports of angioedema (some serious), such as swelling of the face, lips, and/or tongue which may be associated with difficulty breathing or wheezing, have been received in association with use of pirfenidone in the post-marketing setting. Therefore, patients who develop signs or symptoms of angioedema following administration of pirfenidone should immediately discontinue treatment. Patients with angioedema should be managed according to standard of care. Pirfenidone should not be used in patients with a history of angioedema due to pirfenidone treatment. See Sections 5.4.2.16 and 6.4.1 of the Investigator's Brochure for more details.

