5.3.5.1 Diagnosis versus Signs and Symptoms

A diagnosis (if known) should be recorded on the Adverse Event eCRF rather than individual signs and symptoms (e.g., record only liver failure or hepatitis rather than jaundice, asterixis, and elevated transaminases). However, if a constellation of signs and/or symptoms cannot be medically characterized as a single diagnosis or syndrome at the time of reporting, each individual event should be recorded on the Adverse Event eCRF. If a diagnosis is subsequently established, all previously reported adverse events based on signs and symptoms should be nullified and replaced by one adverse event report based on the single diagnosis, with a starting date that corresponds to the starting date of the first symptom of the eventual diagnosis.

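### The angioedema row of the safety overview counts one preferred term, so it can miss patients recorded only by facial, lip or tongue swelling

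*SAP*

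**What the plan says.** SAP v3.0 section 4.6.2 lists the rows of the patient safety overview. The angioedema row is defined as "Angioedema (MedDRA preferred term Angioedema"), and SAP v2.0 section 4.7.2 has the same definition. In the same list, rash and photosensitivity are each built from several preferred terms, and the gastrointestinal row is a whole system organ class.

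Protocol section 5.1.1.4 describes angioedema by how it presents, "such as swelling of the face, lips, and/or tongue which may be associated with difficulty breathing or wheezing", and says that "patients who develop signs or symptoms of angioedema following administration of pirfenidone should immediately discontinue treatment". Protocol section 4.6.2 names angioedema among four events under the rule "Patients must discontinue trial treatment if they experience any of the following".

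Protocol section 5.3.5.1 governs what is written on the adverse event form:

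- Where the diagnosis is known: "A diagnosis (if known) should be recorded on the Adverse Event eCRF rather than individual signs and symptoms".
- Where signs "cannot be medically characterized as a single diagnosis or syndrome at the time of reporting, each individual event should be recorded".
- Where a diagnosis comes later, "all previously reported adverse events based on signs and symptoms should be nullified and replaced by one adverse event report".

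**The concern.** The protocol acts on signs, while the overview counts a diagnosis. A patient can stop drug because of lip or tongue swelling, have that swelling entered as its own event because nobody settles on a diagnosis, and then not be counted in the row that carries the name of the risk.

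The event is rare and some post-marketing reports were serious (protocol section 5.1.1.4), so one or two patients can decide whether the row reads zero. A zero under the present definition is ambiguous: it could mean that no patient had this swelling, or that none had it coded to the one term. What is at stake is how clearly a rare risk is shown by arm. No efficacy result and no hypothesis test is involved.

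**Working it through.** The plan states no figure for this row, so the check is mainly a reading of the rules in sequence.

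**Following one patient through the rules**

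1. Lip swelling appears after dosing. Protocol section 5.1.1.4 stops drug on signs or symptoms; a confirmed diagnosis is not required.
2. If the investigator diagnoses angioedema, at once or later, protocol section 5.3.5.1 puts the diagnosis on the form. The patient is counted. This should be most cases.
3. If no diagnosis is ever made, the same section has each sign entered separately.
4. SAP section 4.6.2 maps each verbatim entry to a preferred term. If lip swelling maps to anything other than Angioedema, the patient is not in the row.

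Step 4 rests on an assumption about the dictionary, which the documents do not reproduce. The SAP's own rash list, which separates many closely related terms, is consistent with it.

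**Where the omitted patient still appears**

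The patient is counted under any treatment-emergent event and under events leading to discontinuation if drug was stopped. The event is also in the class and term tables ("TEAEs leading to treatment discontinuation, dose modification or death will be summarized by treatment arm, by system organ class (SOC) and preferred term (PT") and in the by-patient listing. None of these groups swelling events for this risk.

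**Illustrative size**

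The only input from the documents is 125 planned patients per arm (SAP section 2.3). Assumed inputs are n = 1 or 2 patients with the swelling in an arm, and s = 10% to 50% of them never diagnosed.

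- Expected number omitted = n × s. Lowest: 1 × 0.10 = 0.1. Highest: 2 × 0.50 = 1.0.
- As a share of the arm: 0.1/125 = 0.08% and 1.0/125 = 0.8%.
- Chance that the row shows zero although the cases exist = s^n, taking patients as independent:

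| s | n = 1 | n = 2 |
|---|---|---|
| 0.10 | 10% | 1% |
| 0.25 | 25% | 6.25% |
| 0.50 | 50% | 25% |

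A second set of assumptions starts from a true risk p of 0.5% to 4% and a share c of 25% to 75% coded to the single term. The chance that at least one true case occurs and the row still shows zero is (1 − pc)^125 − (1 − p)^125. At p = 1% and c = 50% this is 0.995^125 − 0.99^125 = 0.534 − 0.285 = 0.25. Over the values tried it runs from 2% (p = 4%, c = 75%) to 45% (p = 2%, c = 25%). It is 0% if every case is coded to the single term.

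The two ranges answer slightly different questions. The first is conditional on cases existing; the second also allows for there being none. Both reflect the assumed inputs and are not evidence of an actual shortfall.

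**The case against.** The strongest reply is that the gap is narrow and its key premise cannot be verified. The recording rule pushes cases towards the diagnosis, and an investigator who stops drug for angioedema has usually already called it that. A history of angioedema is an exclusion criterion. Whether lip swelling maps to a different term is not shown in the documents. All of this stands, and it is why the point is limited to patients never diagnosed and its size is only illustrative.

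Second, the patients are visible elsewhere. Besides the tables above, SAP section 4.4.1 reports reasons for early discontinuation, and protocol section 4.6.2 has the primary reason recorded. This is partial cover, because the reason categories are not given and a patient who was not taken off drug would not be there. No such output collects the events by arm.

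Third, dizziness, fatigue and weight loss are also single-term rows, and protocol section 5.2.3 does not list angioedema as an event of special interest. Both are true, so the format is not an anomaly in the list. Of these four, however, only angioedema is a mandatory reason to stop treatment.

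Fourth, SAP section 4.6.2 says that standardised query lists will be used. That sentence concerns coding in general; it assigns no query to this row, whose definition names one term.

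**Conclusion.** The concern holds as a minor one. Applied as written, the rules can leave a patient with undiagnosed facial, lip or tongue swelling out of the only row named for angioedema. This rests on one assumption, that such a sign is coded to a term other than Angioedema.

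The real shortfall cannot be sized from the documents. On the assumed inputs it would be at most about one patient per arm, and it may well be none. Safety data are not tested formally (SAP section 4.6), so the consequence is confined to how readily a reader can see a rare risk by arm.

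**What to change.** In SAP section 4.6.2, add a grouped angioedema row made up of Angioedema plus the preferred terms for swelling or oedema of the face, lips and tongue. Keep the present single term as a sub-row. Show both in the double-blind overview and in the open-label overview under SAP section 4.7. Someone without access to treatment codes should choose the term list, and the row should be labelled as added after the primary analysis of March 2019 (SAP section 4.5.8).

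The cost is one term list and one table rerun, with no new data. Some non-allergic swelling will be included; the sub-row shows how many patients enter only through the added terms. Editing lists in this block is not a new kind of change. Between v2.0 and v3.0, Nodular rash moved from rash to photosensitivity, and Pruritus allergic, Rash follicular and Exfoliative Rash were dropped.

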5.1.1.7 Weight loss

In the pooled Phase 3 analysis (PIPF-004/006/016), the adverse event of weight decrease was reported for a larger proportion of pirfenidone patients than placebo patients (10.1% pirfenidone vs. 5.4% placebo), and the majority of pirfenidone patients who reported an adverse event of weight decrease first did so during the initial 6 months of treatment (39/63, 61.9%). In the pirfenidone group, two (0.3%) patients had Grade 3 adverse events, one (0.2%) patient had a serious adverse event, and five (0.8%) patients discontinued trial treatment for this adverse event; there were no Grade 4 events, hospitalizations, or deaths. In the placebo group, one (0.2%) patient had a serious adverse event and was hospitalized; there were no Grade 3 or 4 events, deaths, or treatment discontinuations for this adverse event. See Sections 5.4.2.14 and 6.4.1 of the Investigator's Brochure for more details.

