5.2.3 Adverse Events of Special Interest (Immediately Reportable to the Sponsor)

Adverse events of special interest are required to be reported by the investigator to the Sponsor immediately (i.e., no more than 24 hours after learning of the event; see Section 5.4.2 for reporting instructions). Adverse events of special interest for this trial include the following:

- Cases of potential drug-induced liver injury that include an elevated ALT or AST in combination with either an elevated bilirubin or clinical jaundice, as defined by Hy's law (see Section 5.3.5.6)
- Suspected transmission of an infectious agent by the trial treatment, as defined below:

Any organism, virus, or infectious particle (e.g., prion protein transmitting transmissible spongiform encephalopathy), pathogenic or non-pathogenic, is considered an infectious agent. A transmission of an infectious agent may be suspected from clinical symptoms or laboratory findings that indicate an infection in a patient exposed to a medicinal product. This term applies only when a contamination of the trial treatment is suspected.

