5.3.5.6 Abnormal Liver Function Tests

The finding of an elevated ALT or AST ($> 3 \times \text{ULN}$) in combination with either an elevated total bilirubin ($> 2 \times \text{ULN}$) or clinical jaundice in the absence of cholestasis or other causes of hyperbilirubinemia is considered to be an indicator of severe liver injury (as defined by Hy's law). Therefore, investigators must report as an adverse event the occurrence of either of the following:

- Treatment-emergent ALT or AST $> 3 \times \text{ULN}$ in combination with total bilirubin $> 2 \times \text{ULN}$
- Treatment-emergent ALT or AST $> 3 \times \text{ULN}$ in combination with clinical jaundice

The most appropriate diagnosis or (if a diagnosis cannot be established) the abnormal laboratory values should be recorded on the Adverse Event eCRF (see Section 5.3.5.1) and reported to the Sponsor immediately (i.e., no more than 24 hours after learning of the event), either as a serious adverse event or an adverse event of special interest (see Section 5.4.2).

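### SAP 4.6.2 names the weight event by two different terms, and its bracketed Hy's law rule omits clinical jaundice: two minor inconsistencies in descriptive safety outputs

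*SAP*

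**What the plan says.** **Weight.** The patient safety overview in SAP 4.6.2 (version 3.0) has a row defined as "Weight loss (MedDRA preferred term Weight loss", which fixes both the dictionary level and the term. Later in the same section, the Kaplan-Meier curves for time to first onset of the most relevant related events are specified: "These will include the following PTs or groups of AEs: Nausea, Diarrhoea, Weight decreased, Fatigue, Decreased appetite", followed by photosensitivity or rash. Protocol 5.1.1.7 is headed Weight loss, but its text says that "the adverse event of weight decrease was reported for a larger proportion of pirfenidone patients than placebo patients", at 10.1% against 5.4% in the pooled Phase 3 IPF data. For pirfenidone patients only, it adds that the majority "first did so during the initial 6 months of treatment (39/63, 61.9" per cent).

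**Hy's law.** The adverse-event-of-special-interest entry in the overview first describes raised ALT or AST with either raised bilirubin or clinical jaundice. It then closes with a bracketed rule: "ALT or AST >3 x ULN + total bilirubin >2 x ULN". Protocol 5.2.3 defines the event as raised ALT or AST "in combination with either an elevated bilirubin or clinical jaundice". Protocol 5.3.5.6 gives the thresholds, with total bilirubin above 2 x ULN "or clinical jaundice in the absence of cholestasis or other causes of hyperbilirubinemia", and makes ALT or AST above 3 x ULN with clinical jaundice a reportable event in its own right.

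**Hepatic row.** The next overview row is "Any and any related hepatic side effects: elevations in ALT and AST", both above 3 x ULN at the same timepoint.

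**The concern.** Weight decrease is a named pirfenidone risk with a known imbalance against placebo. Two outputs in one section that are meant to show it are keyed to different terms. If coding uses only one of them, a literal match on the other returns few patients or none, and the overview would disagree with the rest of the safety tables.

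The liver definition raises a similar problem. The bracket is the part of the entry that reads like a programming rule, and it is narrower than the sentence it completes and than the protocol definition. A patient with raised ALT or AST and clinical jaundice, but without bilirubin above 2 x ULN, meets the protocol definition and fails the bracket.

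**Working it through.** **1. Weight terms side by side**

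- SAP 4.6.2, overview row: preferred term Weight loss.
- SAP 4.6.2, Kaplan-Meier list: Weight decreased, in a list of preferred terms or groups of events.
- Protocol 5.1.1.7: heading Weight loss; event called weight decrease.

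The SAP spells out term lists for photosensitivity and for rash but none for weight, so Weight decreased cannot be traced to a defined group. Which term is a valid preferred term depends on the MedDRA version used (20.1 or higher), and the documents do not settle that.

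**2. Size, if all weight events are coded to the term the overview row does not use**

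The plan gives no figure to reproduce. Inputs: 10.1% (pirfenidone), 5.4% (placebo) and 39/63 = 61.9% from Protocol 5.1.1.7; 125 per arm from the sample size section.

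- Consistency of the source: 63 / 0.101 = 624 patients; 39 / 624 = 6.25%.
- Pirfenidone: 0.101 x 0.619 = 0.0625; 0.0625 x 125 = 7.8 patients expected. The 2.5th to 97.5th percentiles of Binomial(125, 0.0625) are 3 to 13, and the probability of no event is 0.0003.
- Placebo: 0.054 x 0.619 = 0.0334; 0.0334 x 125 = 4.2 patients, range 1 to 8. The 61.9% is an assumption here, since the protocol gives it only for pirfenidone.
- Time window: 24 x 7 + 28 = 196 days; 196 / 30.4375 = 6.4 months, so a 6-month fraction is a reasonable match.

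These ranges are sampling variation at a fixed, borrowed rate. They do not include uncertainty about carrying an IPF rate into unclassifiable ILD. The Kaplan-Meier list covers related events only, and the documents give no rate for those.

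**3. Hy's law: bracket against protocol rule**

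Take four yes/no facts at one timepoint: ALT above 3 x ULN, AST above 3 x ULN, bilirubin above 2 x ULN, clinical jaundice. There are 2^4 = 16 patterns. The protocol's exclusion of cholestasis and other causes is left aside.

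- Bracket: 3 enzyme combinations x 2 (bilirubin raised, jaundice either way) = 6 patterns.
- Protocol: 3 enzyme combinations x 3 (bilirubin, jaundice, or both) = 9 patterns.
- Missed by the bracket: 9 - 6 = 3, each with jaundice and without bilirubin above 2 x ULN.

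Adding jaundice brings the bracket to 9, equal to the protocol rule. These are logical patterns, not patient frequencies. The documents give no rate, so no number of patients is claimed.

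**4. Paired ALT-and-AST row**

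The paired row covers 1 x 4 = 4 patterns. Of the bracket's 6 patterns, 2 lie inside it and 4 outside. For example, ALT 4, AST 2 and bilirubin 2.5 x ULN meets the bracket but not the paired row. A row for ALT or AST above 3 x ULN would cover 3 x 4 = 12 patterns, including all 9 protocol patterns.

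**The case against.** The strongest case on the other side is that nothing is lost from the safety reporting as a whole, and most of it stands.

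**Weight.** A reader might infer that about 8 pirfenidone patients with weight events would disappear from the safety analysis. The documents do not support that. Every coded event still enters the tables by system organ class and preferred term, the by-grade table and the patient listing (all SAP 4.6.2). Measured weight and its change from baseline are summarised by arm under SAP 4.6.5. An empty overview row would be visible against these. The Kaplan-Meier list also allows groups of events, so Weight decreased could have been meant as a group. What remains is that no such group is defined and the two outputs carry different names.

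**Hy's law.** A reader might infer that jaundice cases will be dropped. The documents do not say so. The overview entry counts any and related events of special interest, and relatedness is an investigator judgement attached to an adverse event record (Protocol 5.3.4). The row is therefore most naturally filled from reported events. Protocol 5.2.3 and 5.3.5.6 require jaundice cases to be reported, and the SAP sentence before the bracket names jaundice. What remains is that the SAP entry contradicts itself in the part most likely to be turned into code.

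**Hepatic row.** A reader might infer that the paired row is wrong because it does not contain every Hy's law case. No passage requires it to. Its pairing of ALT and AST follows Protocol 5.1.1.1; only the same-timepoint condition is the SAP's own. The example patient above, once reported as required, is counted in the special-interest entry directly above that row. Two rows with different definitions may properly give different counts.

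**Conclusion.** Two internal inconsistencies stand, both minor. The weight event is named by different terms in two outputs of SAP 4.6.2, and the Hy's law bracket is narrower than its own sentence and the protocol.

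The weight consequence is conditional. If all events are coded to the term the overview row does not use, about 8 of 125 pirfenidone patients (3 to 13 at the borrowed rate) and about 4 of 125 placebo patients (1 to 8, with the timing fraction assumed) would be absent from one overview row only. If coding follows the overview term, that row is complete and the Kaplan-Meier output is the one affected. The Hy's law consequence arises only if the bracket alone is applied to laboratory data.

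Severity is minor because SAP 4.6 plans no formal testing of safety and the other outputs remain. The absence of any listed output giving the number of patients with ALT or AST above 3 x ULN is a gap worth filling, not an error: the liver tables show CTCAE grade shifts and grade 3-4 results by parameter.

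**What to change.** 1. Verify the weight preferred term in the MedDRA version used. Apply the same term, or the same explicit term list, in the overview row and the Kaplan-Meier output.
2. Complete the Hy's law bracket with the clinical jaundice branch, so that it matches Protocol 5.2.3 and 5.3.5.6. Jaundice is not a laboratory variable, so state that it is taken from the reported adverse event and special-interest records.
3. Optional: keep the paired ALT-and-AST row and add a row for ALT or AST above 3 x ULN.

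The cost is low: one term harmonised, one bracket completed, at most one row added, and the affected outputs re-run. The term-level work is feasible, since version 3.0 of the SAP revised the photosensitivity and rash lists in this section while leaving the weight mismatch. The weight mismatch, the bracket and the paired row were already in SAP version 2.0 of October 2018 (section 4.7.2), and SAP 4.5.8 dates the primary analysis to March 2019. Counts may therefore differ from output already produced, so label the changes post hoc and show both versions.
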